10.4. Safety Analysis

All safety analyses will be performed using the Safety Analysis Set.

If applicable, safety will be evaluated by assessment of clinical laboratory tests, physical examinations, ECGs, vital signs measurements at various time points during the study, and by the documentation of AEs.

All safety data collected on or after study drug administration up to the last scheduled visit, unless specified otherwise, will be summarized by cohort for each VIR-3434 dose and placebo.

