10.4.2. Laboratory Evaluations

Selected laboratory data will be summarized (n, mean, SD, median, Q1, Q3, minimum, and maximum) by cohort and study visit along with corresponding change from baseline. Graded laboratory abnormalities will be defined using CTCAE Version 5.0 grading scale.

The incidence of treatment-emergent laboratory abnormalities, defined as values that increase at least 1 toxicity grade from baseline at any postbaseline timepoint will be summarized by treatment group. If the relevant baseline laboratory data are missing, then any abnormality of at least Grade 1 will be considered as treatment-emergent.

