- ^o Includes samples for ADA and neutralizing antibodies (NAb), as applicable. Additional unscheduled samples for immunogenicity analysis may be collected if an immunologic related event is suspected. Immunogenicity sampling beyond the planned follow-up period may occur based on emerging results. Further details can be found in Section 8.16 .
- ^p Local tolerability only needs to be assessed for subjects who are administered study drug by SC injection. On Day 1, local tolerability should be assessed at approximately 1 hour post-dose. At the discretion of the investigator, unscheduled visits are permitted as needed for follow up of any unresolved local tolerability symptoms.
- ^q All AEs related to screening activities must be collected starting at the time of consent; any other events occurring during the screening period should be reported as medical history. All SAEs must be collected from the time of consent onwards. Further details can be found in Section 9.3.

APPENDIX 3. PART B, C, AND D SCHEDULE OF ASSESSMENTS FOR SAD COHORTS IN SUBJECTS WITH CHRONIC HBV INFECTION WITHOUT CIRRHOSIS

Part B, C, and D														
Study Stage	Screening	Dosing Day ^a	Post-dose Follow-up Period							Extended Follow-up Period ^b				
Study Visit Week					W1		W2	W4	W8/ET ^c	W12	W16	W24	W32	W40 / EF ^d
Study Visit Day±Visit Window	D -42 to -1	D1 ^e	D2	D4+1	D8±1	D11±1	D15±2	D29±2	D57±7	D85 ±7	D113 ±7	D169 ±7	D225 ±7	D281 ±7
Informed consent	X													
Demography	X													
Medical history including HBV genotype ^f	X													
Inclusion/exclusion criteria	X	X ^g												
Full physical examination ^h	X			X					X					
Symptom-directed physical examination		X	X		X		X	X						
Body weight	X													
Height	X													
Vital signs ⁱ	X	X	X	X	X		X	X	X					
Safety ECGs ^j	X													
Pregnancy test ^k	X	X						X	X	X	X	X	X	X
FibroScan ^l	X													
Screening viral serology ^m	X													
Liver Function Tests ⁿ	X	X	X	X	X		X	X	X	X	X	X	X	X
Serum Chemistry ⁿ	X	X	X	X	X		X	X	X	X	X	X	X	X

Part B, C, and D														
Study Stage	Screening	Dosing Day ^a	Post-dose Follow-up Period							Extended Follow-up Period ^b				
Study Visit Week					W1		W2	W4	W8/ET ^c	W12	W16	W24	W32	W40 / EF ^d
Study Visit Day±Visit Window	D -42 to -1	D1 ^e	D2	D4+1	D8±1	D11±1	D15±2	D29±2	D57±7	D85 ±7	D113 ±7	D169 ±7	D225 ±7	D281 ±7
Hematology ⁿ	X	X	X	X	X		X	X	X					
Coagulation Parameters ⁿ	X	X	X	X	X		X	X	X					
Complement testing ^{n,o}		X			X		X							

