6. STATISTICAL ANALYSES

6.1. General Considerations

The study assessments and time points schedule are provided in the study protocol. All individual participant data for those who were randomized to study intervention will be presented in data listings.

Continuous variables will be summarized using the following descriptive summary statistics: the number of participants (n), mean, standard deviation (SD), median, minimum value (min), and maximum value (max), unless otherwise specified.

In general, the precision of the measurement for each continuous variable will be used to determine the number of decimal places to present in tables, figures, and derived listings. Unless otherwise specified, raw data will be presented with the same number of decimals as collected, and derived data will be presented with an appropriate number of decimals based on general practice, mathematical rationale, or scientific rationale. Any values that require transformation to standard units (metric or SI) will be converted with the appropriate corresponding precision.

Categorical variables will be summarized using counts and percentages. Generally, percentages will be presented to 1 decimal place.

Baseline Value: Unless otherwise specified, the baseline value will be defined as the most recent non-missing (scheduled or unscheduled) measurement collected prior to the administration of study intervention.

If multiple measurements that are prior to dosing are recorded on the same date and with the same time or if time is not available, then the average of these measurements will be considered the baseline value.

Absolute change from baseline will be calculated as post-baseline value - baseline value.

Treatment-emergent (TE) period: Unless otherwise specified, the TE period will include the time from the administration of study drug until the Week 24 visit (or the Day 169, if the Week 24 visit is unavailable) for Part A, and the Week 8 visit (or the Day 57, if the Week 8 visit is unavailable) for Part B, C, and D.

Unscheduled visits: Unscheduled visit measurements will be included in analysis as follows:

1. In scheduled visit windows per specified visit windowing rules, if applicable
2. In the derivation of baseline and last follow-up measurements
3. In the derivation of maximum and minimum values and/or maximum and minimum change from baseline values during follow-up period or TE period
4. In individual participant data listings as appropriate

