6.4. Safety Analyses

Safety analyses will be based on data from the TE Period for all participants in the Safety Analysis Set, unless otherwise specified. All safety data will be included in the individual participant listings. Participants will be analyzed according to the treatment dose level they received.

The overall safety profile of the study intervention will be assessed in terms of the following safety and tolerability assessments:

- TEAEs
- Clinical laboratory
- ECG
- Vital signs
- Physical examination

Only descriptive analysis of safety will be performed, and no statistical testing will be performed.

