6.4.2. Clinical Laboratory

Clinical laboratory data collected (through central laboratories only, unless otherwise specified) will be analyzed using both quantitative and qualitative methods and presented by VIR-3434 treatment cohort and placebo, for each of Part A, B, C, and D. The analysis will be based on values reported in conventional units.

For the treatment-emergent laboratory measurements, the observed values and change from baseline values of the continuous hematology, serum chemistry, and coagulation results will be summarized descriptively (n, mean, SD, median, min, max) at each visit.

For ALT, AST, total bilirubin, lymphocytes, neutrophils, platelets, and INR, mean (\pm SD) of the observed values will be plotted by visit and by each VIR-3434 treatment cohort and placebo for each of Part A, B, C, and D.

The Common Terminology Criteria for Adverse Events (CTCAE, v5.0) will be used as the reference on grading scale to assign severity (toxicity) grades (1 to 4) to abnormal results for the laboratory of interest as shown in Appendix 5. Grade 0 refers to the normal values that do not meet the criteria of laboratory abnormalities.

For treatment-emergent laboratory abnormalities, the number and percentage of participants who met at least 1 threshold criterion of severity grade will be summarized by VIR-3434 treatment cohort and placebo for each of Part A, B, C, and D, based on the most severe postdose abnormality grade during TE period for a given laboratory test. The threshold of severity grade shifted from baseline will also be summarized for selected laboratory tests.

In addition, a separate listing containing individual participants with hematology, chemistry, coagulation, and urinalysis values will be provided based on the Safety Analysis Set by subject ID and visit in chronological order including data collected from both scheduled and unscheduled visits. Values falling out of the relevant normal range (between the value of LLN and ULN) or having the severity grade of 1 or higher on laboratory abnormalities will be flagged as appropriate.

Results of positive urine/serum pregnancy test will be listed in an individual participant data listing only.

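### SAP 6.4.2 counts treatment-emergent laboratory abnormalities without the protocol's condition of a grade rise from baseline; separately, the hyperkalaemia Grade 2 band in SAP Appendix 5 does not fit its neighbours

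*SAP*

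**What the plan says.** Protocol 10.4.2 plans an incidence table of treatment-emergent laboratory abnormalities, "defined as values that increase at least 1 toxicity grade from baseline at any postbaseline timepoint". It adds a rule for missing baseline: "If the relevant baseline laboratory data are missing, then any abnormality of at least Grade 1 will be considered as treatment-emergent".

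SAP 6.4.2 keeps the label but writes a different counting rule: "For treatment-emergent laboratory abnormalities, the number and percentage of participants who met at least 1 threshold criterion of severity grade will be summarized", "based on the most severe postdose abnormality grade during TE period for a given laboratory test". That rule mentions neither a baseline grade nor a missing baseline. The same section then adds grade shift from baseline as a further output, for selected tests that it does not name. It also plans change-from-baseline summaries, mean plots for some tests, and a listing that flags out-of-range or graded values.

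SAP 6.8.1 lists five departures from the protocol. The only one on safety limits TEAEs to the TE period. Nothing there mentions the grade-rise condition for laboratory tests.

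SAP Appendix 5 prints the hyperkalaemia grades (mEq/L) as: Grade 1, above ULN to 5.5; Grade 2, above 6.0 to 6.5; Grade 3, above 6.0 to 7.0; Grade 4, above 7.0.

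**The concern.** Two programmers could build different tables from the same SAP text. One would read *treatment-emergent* as the protocol defines it and require a grade rise. The other would follow the written rule and count every participant with a graded postdose value. Under the second reading, a Part D participant whose ALT falls from 4×ULN to 2×ULN is tabulated as a treatment-emergent abnormality.

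The SAP's own usage makes the second reading reasonable. It applies the term to laboratory and vital-sign measurements (6.4.2, 6.4.4), where it can only refer to timing. Where it means worsening, as for TEAEs in 6.4.1, it says so.

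Laboratory abnormalities are a primary endpoint (Protocol 4.1 and 4.2), and hepatotoxicity is a named potential risk in Parts B–D (Protocol 2.4). A liver-test table that mixes pre-existing and new grades under this label would be hard to interpret.

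The potassium row raises a separate problem. A value of 5.5 mEq/L is Grade 1, but a higher value of 5.8 mEq/L meets no grade at all.

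**Working it through.** **1. The two counting rules.** Let *b* be the baseline grade and *w* the worst postdose grade within the same window.

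- Protocol 10.4.2: count if *w* ≥ *b* + 1; if baseline is missing, count if *w* ≥ 1.
- SAP 6.4.2 as written: count if *w* ≥ 1.

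If *w* ≥ *b* + 1 then *w* ≥ 1, so the literal SAP rule never misses a protocol case within its window. It can only add cases, namely those with 1 ≤ *w* ≤ *b*. When *b* = 0 or baseline is missing, the rules agree.

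**2. Which baseline grades can occur.** Set the eligibility limits (Protocol 6.5) against the grades in SAP Appendix 5:

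- ALT/AST, Parts B and C: excluded above 2×ULN, so *b* can be 1 (Grade 1 runs to 3×ULN).
- ALT/AST, Part D: excluded above 5×ULN, so *b* can be 2 (Grade 2 runs to 5×ULN).
- Neutrophils, Parts B–D: benign ethnic neutropenia above 1,200 cells/µL (1.2 × 10⁹/L) is allowed. Values below 1.5 × 10⁹/L are Grade 2.
- Creatinine clearance, Parts B–D: excluded below 60 mL/min. From 60 mL/min to LLN is Grade 1.
- GGT and glucose, among others: graded in Appendix 5 but with no numeric screening limit.

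Appendix 5 grades ALT and AST by multiples of ULN only, so the grade itself does not bring in baseline.

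**3. Where the rules differ for ALT/AST**, if Day 1 grades stay within the screening limits:

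- Parts B and C (*b* ≤ 1): only at (*b*, *w*) = (1,1).
- Part D (*b* ≤ 2): at (1,1), (2,1) and (2,2).

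Examples at or before Week 8:

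| Baseline ALT | Worst postdose ALT | Protocol | SAP literal |
|---|---|---|---|
| 1.5×ULN (Grade 1) | 1.5×ULN (Grade 1) | no | yes |
| 4×ULN (Grade 2) | 4×ULN (Grade 2) | no | yes |
| 4×ULN (Grade 2) | 2×ULN (Grade 1) | no | yes |
| 1.5×ULN (Grade 1) | 4×ULN (Grade 2) | yes | yes |

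No such bound applies to tests without a screening cap, because *b* is then not limited by eligibility.

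**4. Weight of one case.** With 6 active participants per cohort (Protocol Tables 3–6), one case is 1/6 = 16.7 percentage points. Placebo is pooled by Part and route (Protocol synopsis). With 2 placebo participants in each Part B–D cohort marked enrolled in SAP Table 2, the planned pools are 4 × 2 = 8 (B), 3 × 2 = 6 (C) and 2 × 2 = 4 (D). One case is then 12.5, 16.7 or 25.0 points.

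**5. Hyperkalaemia row.**

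| Potassium (mEq/L) | As printed | With Grade 2 = >5.5–6.0 |
|---|---|---|
| 5.6, 5.8, 6.0 | no grade | 2 |
| 6.1, 6.3, 6.5 | 2 and 3 | 3 |
| 6.6, 7.0 | 3 | 3 |
| 7.1 | 4 | 4 |

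As printed, every value in the Grade 2 band is also Grade 3, so a worst-grade rule never assigns Grade 2.

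**The case against.** **The label may import the protocol definition.** SAP 1 says the plan is based on the current protocol, so 6.4.2 might describe only how to tabulate abnormalities already defined there. This is possible, and it makes the fault one of unclear text rather than a proven change of definition. But the SAP does not say so, and its own use of the term points to timing.

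**The consequences are limited.** Safety analysis is descriptive, there are no hypotheses, cohorts are small, and all safety data are listed. All of this stands. The shift summary helps only for the tests that are selected.

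**A reader might infer that the primary endpoint is miscounted.** The documents do not support that. The endpoint is worded as subjects with laboratory abnormalities, without a grade-rise condition, so the literal count still fits it. Only the table labelled treatment-emergent is ambiguous.

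**A reader might infer that Grade 3–4 counts are safe for every test.** That follows only for tests with a suitable screening cap, such as ALT/AST, and only if Day 1 grades respect it.

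**A reader might infer that the Week 8 cut-off is an undisclosed departure.** In Parts B–D, liver tests and chemistry continue at five visits after Week 8 (Protocol Appendix 3), and Protocol 10.4.2 speaks of any postbaseline timepoint. But Protocol 10.4 leaves room for another window: "All safety data collected on or after study drug administration up to the last scheduled visit, unless specified otherwise, will be summarized by cohort". The SAP uses that room openly: "Safety analyses will be based on data from the TE Period for all participants in the Safety Analysis Set, unless otherwise specified", with the period ending at the "Week 8 visit (or the Day 57, if the Week 8 visit is unavailable) for Part B, C, and D". The 6.8.1 row gives the reason for the period and cites Section 6.4, though its text names only AEs. Extended follow-up is limited to participants with a >2-fold HBsAg reduction at Week 8, and it can end on rebound or at the sponsor's discretion. A count table there would describe a response-selected subset. Whether to tabulate it is the sponsor's choice, not an error.

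**On potassium,** the worst-grade rule settles the overlap as Grade 3, and listings still flag out-of-range values. The gap remains. A text-extraction fault in that one cell cannot be excluded.

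**Conclusion.** The point holds in two limited parts.

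First, SAP 6.4.2 states a counting rule without the baseline comparison that Protocol 10.4.2 requires, and SAP 6.8.1 does not declare the difference. Applied literally, it adds participants with stable or improved baseline abnormalities and, within the TE period, removes none. For ALT/AST the effect is confined to Grades 1–2, provided Day 1 grades stay within the screening limits. For tests without a numeric cap no bound can be given. How many participants are affected cannot be derived from the documents. One case moves an active cohort by 16.7 points, assuming the planned 6 per cohort.

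Second, the hyperkalaemia row as printed has one 0.5 mEq/L band with no grade and one with two grades. Few participants are likely to be affected, because out-of-range potassium is an exclusion at screening. It is still an operative threshold, and it is wrong as printed.

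**What to change.** **SAP 6.4.2.** Add one sentence: *A participant is counted as having a treatment-emergent abnormality for a test if the worst postdose grade in the TE period is at least 1 grade above the baseline grade, or is Grade 1 or higher if baseline is missing.*

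**SAP Appendix 5.** Check the hyperkalaemia row in the source table and against the CTCAE v5.0 that the SAP cites. Then set Grade 2 to the band that joins the printed Grades 1 and 3, >5.5–6.0 mEq/L.

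**Optional.** Extend the TE-period row in SAP 6.8.1 to say that the limit also applies to laboratory data.

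The cost is one sentence and one table cell, plus a few words in 6.8.1 if the optional change is made. No new data are needed: baseline values are already required for the change-from-baseline and shift summaries, and the same Appendix 5 thresholds grade them. If the sponsor does want every graded postdose value counted, the table title should drop the treatment-emergent label and 6.8.1 should declare the change.

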6.4.3. Electrocardiogram

An individual listing containing ECG measurements including data from both scheduled and unscheduled visit will be provided based on the Safety Analysis Set and presented by subject ID, visit in chronological order. The abnormal assessment with clinical significance will be flagged as appropriate.

6.4.4. Vital Signs

For the treatment-emergent vital signs measurements, the observed values and change from baseline values will be summarized at each visit by VIR-3434 treatment cohort and placebo, for each of Part A, B, C, and D. The following vital signs parameters will be included: systolic and diastolic blood pressure (mm Hg), body temperature ($^{\circ}$ C), pulse rate (beats per minute [bmp]), and respiratory rate (breaths per minute).

An individual participant listing will be provided using data collected from both scheduled and unscheduled visits.

6.4.5. Physical examination

Physical examination findings will be presented as an individual participant data listing only.

6.5. Pharmacokinetics Analysis

All analyses and summaries of PK serum concentrations and PK parameters will be based on the PK Analysis Set and presented by VIR-3434 treatment cohort and placebo, for each of Part A, B, C, and D. Blood samples of VIR-3434 will be obtained from each participant prior to study drug administration and at selected times after study drug administration as outlined in the study protocol.

Standard non-compartmental methods will be used to estimate PK parameters based on VIR-3434 concentration data using Phoenix WinNonlin® software (Version 8.3.5 or higher). The linear/log trapezoidal rule will be used in conjunction with dosing time, serum concentration, and corresponding real-time values. If the real sampling time will not be recorded or will be missing, the planned time will be used for this time point instead.

For concentration data, values reported below the quantitation limit (BQL) will not be imputed in summary statistics with only the number of participants who have non-missing quantifiable results included at each time point.

For estimation of PK parameters, samples BQL prior to the first quantifiable concentration will be set to a concentration value of zero, and BQL values that occur after the first quantifiable point will be considered as missing data.

If a missing value is reported due to no valid or missing of sample result in summary of concentration data and PK parameters, it will be presented as not reported “NR” and excluded from PK analyses and not imputed at any time points. The actual reported values will be provided in individual participant listings.

Natural logarithm transformation may be used for analysis of PK parameters. PK parameters that are BQL will be imputed before log transformation or statistical model fitting. If untransformed value is BQL, the corresponding log transformed value will be zero.

The precision of data reporting in both PK concentrations and PK parameters will follow the below rules:

- 3 significant figures in the same units as the laboratory source data in ng/mL
- 3 significant figures for descriptive statistics except for
 - 4 significant figures for standard deviation
 - percentage to 1 decimal place for CV% and Geometric CV%

6.5.1. PK Variables

PK variables include individual concentration measurements for VIR-3434 following the collection times provided in the study protocol, and the estimated PK parameters in evaluation of PK objectives including but not be limited to:

	PK Parameters
Part A	C_{max} , C_{last} , T_{max} , T_{last} , AUC_{inf} , AUC_{last} , $\%AUC_{exp}$, $t_{1/2}$, λ_z , V_z (IV only), CL (IV only), V_z/F (SC only), and CL/F (SC only)

Part B, C, and D	C_{max} , C_{last} , T_{max} , T_{last} , AUC_{inf} , AUC_{last} , $\%AUC_{exp}$, $t_{1/2}$, λ_z , V_z/F , and CL/F
------------------	---

Definition of selected PK parameters:

Symbol	Definition
C_{max}	Maximum observed concentration of drug following a dose
C_{last}	Last measurable observed concentration of drug following a dose
T_{max}	Time at which maximum concentration of drug is observed
T_{last}	Time at which last measurable concentration of drug is observed
AUC_{last}	Area under the concentration-time curve from time “0” to the last measured timepoint
AUC_{inf}	Area under the concentration-time curve from time “0” to time infinity
$\%AUC_{exp}$	Percent of the area under the concentration-time curve extrapolated from the last measured timepoint to time infinity
$t_{1/2}$	Terminal elimination half-life
λ_z	Terminal elimination rate constant
V_z	Volume of distribution during the terminal elimination phase
CL	Total body clearance
V_z/F	Apparent volume of distribution during the terminal elimination phase, measured after extravascular dosing
CL/F	Total body clearance measured after extravascular administration

The apparent terminal-phase elimination rate constant (λ_z) will be estimated by log-linear regression of the concentration-time data associated with this phase. The decision as to which data points describe the terminal elimination phase will be reached by inspecting the semilogarithmic plot of the data, only considering concentrations at time points beyond T_{max} . λ_z is considered to be well-estimated if a minimum of three data points is used, these data points cover a time span of 2 or more elimination half-lives, and the r^2 value of λ_z is ≥ 0.80 . In cases where λ_z is poorly estimated (i.e., a span of < 2 half-lives or $r^2 < 0.80$), λ_z and the related parameters (AUC_{inf} , CL/F , V_z/F , and $t_{1/2}$) will be flagged in the report and may be excluded from the calculation of summary statistics at the discretion of the clinical pharmacologist.

AUC will be computed using the linear up, log down trapezoidal rule. AUC_{inf} is considered to be well-estimated if $\%AUC_{exp} \leq 20\%$. In cases where $\%AUC_{exp} > 20\%$, AUC_{inf} and the related parameters CL/F and V_z/F will be presented in listings but may be excluded from the calculation of summary statistics at the discretion of the clinical pharmacologist. The nominal time point for a key event or dosing interval (τ) may be used to permit direct calculation of AUC over specific

time intervals. The appropriateness of this approach will be assessed by the clinic pharmacologist on a profile-by-profile basis.

